7.4.2. Laboratory Parameters by Visit

- Summaries will be presented by parent randomized treatment group, and total Safety population.
 - Note: immunoglobulin data will be summarized for subjects from each parent study separately.
- The absolute values and the change from baseline for each analyte will be summarized using descriptive statistics, at each belimumab visit.
- Line graphs will display the time course for each analyte, separately for the absolute value and the change from baseline.

7.4.3. Worst laboratory toxicity grade post-baseline

• Toxicity grading for each analyte will be summarized. This reflects the worst grade for each analyte across all subjects and all assessments for each year interval and at any time post-baseline. The display will summarize the number (%) of subjects for each of the toxicity grades.

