2.2. Study Objective(s) and Endpoint(s)

Objectives	Endpoints	
Primary Objectives	Primary Endpoints	
Evaluate long-term safety and tolerability of belimumab in subjects with SLE in Japan and Korea	The endpoints below will be used to assess this study objective.	
	Adverse events (AEs)	
	 Frequency and percentage of subjects with events. Event rates adjusting for person-years on study agent. Laboratory Parameters Observed and Change from Baseline by visit. Laboratory reference shifts from baseline by visit. Laboratory toxicity worsening of at least two grades from baseline by study year Grade 3 or 4 laboratory abnormalities by visit and study year. 	
	Immunogenicity	
	Immunogenic response (anti-belimumab anti-bodies) by visit and study year.	
	Biomarkers	

[figure not shown]
Objectives	Endpoints
Coonday Objectives	 Percent change from baseline in immunoglobulins, auto-antibodies, and complement levels by visit. Immunoglobulin values below the lower limit of normal by visit and study year. Percent change from baseline in absolute B cell subsets.
Secondary Objectives	SRI and Other Secondary Endpoints
Evaluate the long-term efficacy of belimumab in subjects with SLE in Japan and Korea	SRI response rate at each scheduled visit when complete efficacy evaluations occur (e.g., Week 24 and Week 48 for each year). An SRI response is defined as
	 ≥4 point reduction from baseline in SELENA SLEDAI score, AND
	No worsening (increase of <0.30 points from baseline) in Physician's Global Assessment (PGA), AND
	 No new BILAG A organ domain score or 2 new BILAG B organ domain scores compared with baseline at the time of assessment.
	 Percent of subjects with ≥4 point reduction from baseline in SELENA SLEDAI score assessed every 24 weeks Percent of subjects with No Worsening in PGA compared
	to baseline (added to the RAP)
	Percent of subjects with No new BILAG A organ domain or 2 new BILAG B organ domain scores compared to baseline (added to the RAP)
	 Number of days of daily prednisone dose ≤ 7.5 mg/day
	and/or reduced by 50% from baseline over time.
	Time to first severe SLE Flare Index (SFI) flare assessed over time.
	Other Efficacy Endpoints
	Disease Activity
	Absolute change and percent change from baseline in SELENA SLEDAI (added to the RAP)
	Change in Systemic Lupus International Collaborating Clinics (SLICC)/ACR Damage Index assessed every 24 weeks.
	SLICC/ACR Damage Index Worsening from baseline (added to the RAP).

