7.4.4. Shift in Laboratory toxicity grade post-baseline

- Toxicity grade shifts from baseline of ≥ 2 grades for each analyte will be summarized for each year interval and at any time post-baseline. The display will summarize the number (%) of subjects with at least one ≥ 2 grade shift as well as the specific shift categories: Grade 0 to 2, Grade 0 to 3, Grade 0 to 4, Grade 1 to 3, Grade 1 to 4, and Grade 2 to 4.
- See Appendix 2: Assessment Windows for handling of the post-last dose 16 Week follow-up visit.

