7.4.5. Laboratory Reference Range Shifts

- Summaries will be presented by parent randomized treatment group, and total Safety population.
- Laboratory reference range shifts will be summarized only for laboratory tests without toxicity grades.
- A laboratory value that is outside of normal range will be considered abnormal (above or below).
- Shifts relative to the normal range will be summarized for each analyte, at each belimumab visit, as follows:
 - o 'n' represents the number (%) of subjects with a low, high or normal value at the specified visit.
 - o For subjects with a low value at the specified visit, the shift categories relative to baseline are shown as either remained low, or normal/high to low.
 - o For subjects with a high value at the specified visit, the shift categories relative to baseline are shown as either remained high, or normal/low to high.

 For subjects with a normal value at the specified visit, the shift categories relative to baseline are shown as either remained normal, or high to normal, or low to normal.

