11.2.1. Year Intervals

- To report subject disposition and AE assessments with similar durations of exposure to active belimumab treatment, assessments will be slotted into year intervals using a 365-day calendar year.
- Few subjects are expected to have > 6 years exposure and therefore "Year 6+" will be extended to the last available visit.
- For subjects who withdraw during an interval, the end date of their final interval will be set to their exit visit date.
- For summaries, the "Any Time Post-Baseline" includes the follow-up visits, where follow-up visits are excluded from the "Year 6+" year interval.
- For laboratory assessments, the worst value/highest toxicity reported over the year
 interval will be used in the analyses. Concomitant medications will be reported by
 what medications a subject is taking during the interval. In addition, AEs will be
 reported by start date. Subject disposition, worst value/highest toxicity laboratory
 assessments, concomitant medications, and AEs will be summarized according to the
 following year categories.

Study Year	Belimumal	o Study Days
	Start Day	End Day
Year 0-1	Day 1 ^[1] First Treatment Date	Day 365
Year 1-2	Day 366	Day 730
Year 2-3	Day 731	Day 1095
Year 3-4	Day 1096	Day 1460
Year 4-5	Day 1461	Day 1825
Year 5-6	Day 1826	Day 2190
Year 6+	Day 2191	Maximum Study Day [2]

NOTES:

- [1] Protocols specify Day 0 as First Treatment, but due to CDISC standard implementation first treatment date will appear as Day 1 in the analyses. Also, first treatment date refers to first belimumab treatment, regardless of originally randomized treatment.
- [2] Last visit date will be defined as the exit visit date where applicable. Subjects who do not have an exit visit date and only a follow up date, the date of the follow up will be used. See Section 11.5.1 for more details.

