2.48.	Safety	SAFE_T15	Adverse Events of Special Interest Rates per 100 Person-Years by Category					
2.49.	Safety	SAFE_T16	Malignant Neoplasm Adverse Events of Special Interest Rates per 100 Person-Years by Category and PT					
2.50.	Safety	SAFE_T16	Post-Infusion Systemic Reaction Adverse Events of Special Interest Rates per 100 Person-Years by Category and PT					
2.51.	Safety	SAFE_T16	Serious Post-Infusion Systemic Reaction Adverse Events of Special Interest Rates per 100 Person-Years by Category and PT					

Safety	: Tables				
No.	Population	Example Shell	Title	Programming Notes	Final Deliverable [Stage]
2.52.	Safety	SAFE_T16	Infection Adverse Events of Special Interest Rates per 100 Person-Years by Category and PT		
2.53.	Safety	SAFE_T16	Serious Infection Adverse Events of Special Interest Rates per 100 Person-Years by Category and PT		
2.54.	Safety	SAFE_T16	Infection Adverse Events of Special Interest Leading to Permanent Discontinuation of Study Drug or Withdrawal from Study Rates per 100 Person-Years by Category and PT		
2.55.	Safety	SAFE_T16	Depression/Suicide/Self-injury Adverse Events of Special Interest Rates per 100 Person-Years by Category and PT		
Labora	tory				
2.56.	Safety	SAFE_T17	Laboratory Results (Observed and Change from Baseline) by Belimumab Visit: Hematology		
2.57.	Safety	SAFE_T17	Laboratory Results (Observed and Change from Baseline) by Belimumab Visit: Liver Function		
2.58.	Safety	SAFE_T17	Laboratory Results (Observed and Change from Baseline) by Belimumab Visit: Electrolytes		
2.59.	Safety	SAFE_T17	Laboratory Results (Observed and Change from Baseline) by Belimumab Visit: Other Chemistries		
2.60.	Safety	SAFE_T17	Laboratory Results (Observed and Change from Baseline) by Belimumab Visit: Immunoglobulins (Subjects from Parent Study BEL113750)		
2.61.	Safety	SAFE_T17	Laboratory Results (Observed and Change from Baseline) by Belimumab Visit: Immunoglobulins (Subjects from Parent Study BEL112341)		
Worst	Laboratory Tox	icity Grade (by Ye	ar Interval)		

Safety	Safety : Tables								
No.	Population	Example Shell	Title	Programming Notes	Final Deliverable [Stage]				
2.62.	Safety	SAFE_T18	Worst Laboratory Toxicity Grade by Year Interval: Hematology						
2.63.	Safety	SAFE_T18	Worst Laboratory Toxicity Grade by Year Interval: Liver Function						
2.64.	Safety	SAFE_T18	Worst Laboratory Toxicity Grade by Year Interval: Electrolytes						
2.65.	Safety	SAFE_T18	Worst Laboratory Toxicity Grade by Year Interval: Other Chemistries						

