2.66.	Safety	SAFE_T18	Worst Laboratory Toxicity Grade by Year Interval: Urinalysis						
2.67.	Safety	SAFE_T18	Worst Laboratory Toxicity Grade by Year Interval: Immunoglobulins						
2.68.	Safety	SAFE_T19	Laboratory Toxicity Grade Worsening of at Least 2 Grades from Baseline by Year Interval: Hematology						
2.69.	Safety	SAFE_T19	Laboratory Toxicity Grade Worsening of at Least 2 Grades from Baseline by Year Interval: Liver Function						
2.70.	Safety	SAFE_T19	Laboratory Toxicity Grade Worsening of at Least 2 Grades from Baseline by Year Interval: Electrolytes						
2.71.	Safety	SAFE_T19	Laboratory Toxicity Grade Worsening of at Least 2 Grades from Baseline by Year Interval: Other Chemistries						
2.72.	Safety	SAFE_T19	Laboratory Toxicity Grade Worsening of at Least 2 Grades from Baseline by Year Interval: Urinalysis						
2.73.	Safety	SAFE_T19	Laboratory Toxicity Grade Worsening of at Least 2 Grades from Baseline by Year Interval: Immunoglobulins						
Labora	tory Reference	Range Shifts (by	Visit)						
2.74.	Safety	SAFE_T20	Laboratory Reference Range Shifts from Baseline by Belimumab Visit: Hematology						

Safety	: Tables				
No.	Population	Example Shell	Title	Programming Notes	Final Deliverable [Stage]
2.75.	Safety	SAFE_T20	Laboratory Reference Range Shifts from Baseline by Belimumab Visit: Liver Function		
2.76.	Safety	SAFE_T20	Laboratory Reference Range Shifts from Baseline by Belimumab Visit: Electrolytes		
2.77.	Safety	SAFE_T20	Laboratory Reference Range Shifts from Baseline by Belimumab Visit: Other Chemistries		
2.78.	Safety	SAFE_T20	Laboratory Reference Range Shifts from Baseline by Belimumab Visit: Urinalysis		
2.79.	Safety	SAFE_T20	Laboratory Reference Range Shifts from Baseline by Belimumab Visit: Immunoglobulins (Subjects from Parent Study BEL113750)		
2.80.	Safety	SAFE_T20	Laboratory Reference Range Shifts from Baseline by Belimumab Visit: Immunoglobulins (Subjects from Parent Study BEL112341)		
lmmun	ogenicity			•	
2.81.	Safety	SAFE_T21	Immunogenic Response by Belimumab Visit		
2.82.	Safety	SAFE_T22	Immunogenic Response by Year Interval		
2.83.	Safety	SAFE_T23	Immunogenic Summary	See 3750 DB, DS Table 3.73	
Vital Si	gns				
2.84.	Safety	SAFE_T24	Vital Signs by Belimumab Visit		
2.85.	Safety	SAFE_T24	Weight (kg) by Belimumab Visit (Subjects from Parent Study BEL113750)		
2.86.	Safety	SAFE_T24	Weight (kg) by Belimumab Visit (Subjects from Parent Study BEL112341)	_	

CONFIDENTIAL

BEL114333

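### By-year laboratory grade tables pool 4 to 14 scheduled haematology/chemistry looks in the first belimumab year but mostly 2 later, so percentages tend to fall at constant risk, and the by-visit Grade 3 or 4 summary is missing

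*SAP*

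**What the plan says.** SAP 2.2 lists two graded laboratory endpoints under the primary objective: "Laboratory toxicity worsening of at least two grades from baseline by study year" and "Grade 3 or 4 laboratory abnormalities by visit and study year".

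For the first display, SAP 7.4.3 says: "This reflects the worst grade for each analyte across all subjects and all assessments for each year interval and at any time post-baseline". For the second, SAP 7.4.4 says that shifts of two or more grades "will be summarized for each year interval and at any time post-baseline". SAP 11.2.1 defines the years as consecutive 365-day blocks from the first belimumab dose and takes "the worst value/highest toxicity reported over the year" interval. Parent-study laboratory data count from the first belimumab dose (SAP 2.4.1).

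Appendix 12 carries this out in Tables 2.62 to 2.73, for example "Worst Laboratory Toxicity Grade by Year Interval: Hematology" and "Laboratory Toxicity Grade Worsening of at Least 2 Grades from Baseline by Year Interval: Hematology". The by-visit shift tables (2.74 to 2.80) do not fill the gap, because of SAP 7.4.5: "Laboratory reference range shifts will be summarized only for laboratory tests without toxicity grades".

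**The concern.** A maximum over a year depends on how often the subject was sampled in that year. Sampling was about monthly in the double-blind parent studies, less frequent in the first year of BEL114333, and every 24 weeks after that. The dense sampling therefore falls in the early belimumab years. Protocol 3.1 itself says that laboratory frequency was reduced compared with both parent studies. The SAP text attaches no count of assessments and no caveat to the by-year grade tables. The mock shells are a separate document and were not available.

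A reader of Tables 2.62 to 2.73 could take a schedule-driven fall as improving long-term laboratory safety. If the tables are split by parent randomised group, as SAP 2.4.1 and the introduction to 7.4 allow, the early-year comparison between groups also rests on unequal looks. In addition, the by-visit half of the Grade 3 or 4 endpoint has no summary table at all.

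**Working it through.** The plan gives no figure to reproduce, so the check starts from the schedules.

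**Inputs.** Post-baseline haematology/chemistry visits are:
- BEL113750 double-blind: Weeks 2, 4, 8 and every 4 weeks to 52 (SAP 11.1.2.1).
- BEL112341 double-blind: every 4 weeks to Week 52 (11.1.2.2.1). Its open-label phase: Day 168 only (11.1.2.2.2).
- BEL114333: Weeks 4, 12, 24, 36 and 48, then every 24 weeks (protocol 3.1; Tables 2 and 3).

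**Count.** Analysis day = protocol day + 1 (SAP 11.2.1, note 1). Years run 1-365, 366-730, 731-1095 and 1096-1460. Exit, follow-up and unscheduled tests are left out. For BEL113750 belimumab, Year 0-1 holds Days 15, 29, 57 and so on every 28 days to 365 (14 looks). Year 1-2 holds Days 393, 449, 533, 617 and 701. Year 2-3 holds Days 869 and 1037.

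| Cohort (parent randomisation) | Year 0-1 | 1-2 | 2-3 | 3-4 |
|---|---|---|---|---|
| BEL113750 belimumab | 14 | 5 | 2 | 2 |
| BEL113750 placebo | 5 | 2 | 2 | 2 |
| BEL112341 belimumab | 13 | 4 | 3 | 2 |
| BEL112341 placebo | 4 | 3 | 2 | 2 |

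Week 52 falls on Day 365, so a late visit moves one look into Year 1-2. Among visits mapped in SAP 11.2.2, BEL113750 placebo has 2 looks in Year 5-6. BEL112341 placebo has none in Year 4-5: its mapping ends at 168 + 3 × 336 + 224 = Day 1400, and that year starts at Day 1461.

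Other graded tests differ. IgG has 3 to 6 looks in Year 0-1 and 1 per year from Year 2-3. Spot urine protein:creatinine falls from 13 to 2 in the belimumab-randomised cohorts but is 2 in every year for the placebo-randomised cohorts, so no fall is built in there.

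**Size, on assumed values.** The documents give no rates. Assume a constant point prevalence π = 1% and exponential episodes of mean D weeks. With gaps g between looks in weeks,

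P(at least one positive look) = 1 − (1−π) × Π[1 − π(1 − exp(−g/(D(1−π))))].

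For BEL113750 belimumab with D = 12, Year 0-1 has one 2-week gap and twelve 4-week gaps: 1 − 0.99 × 0.99845 × 0.99714^12 = 4.49%. Year 2-3 has one 24-week gap: 1 − 0.99 × 0.99133 = 1.86%. The ratio is 2.42. Year 0-1 to Year 2-3 ratios for all cohorts:

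| Cohort | D = 4 | 12 | 26 | 52 weeks |
|---|---|---|---|---|
| BEL113750 belimumab | 4.36 | 2.42 | 1.73 | 1.40 |
| BEL113750 placebo | 2.33 | 1.80 | 1.48 | 1.28 |
| BEL112341 belimumab | 2.84 | 1.75 | 1.37 | 1.20 |
| BEL112341 placebo | 1.72 | 1.29 | 1.11 | 1.04 |

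The fall need not be steady: BEL112341 placebo at D = 12 gives 2.39%, 2.48% and 1.86% over the first three years. Fully independent samples are the extreme case: (1 − 0.99^14)/(1 − 0.99^2) = 13.1%/2.0%, a ratio of 6.6.

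**Unscheduled tests.** For BEL113750 belimumab at D = 12, the chance of any episode in a year is 1 − 0.99 × exp(−0.01 × 52.14/(0.99 × 12)) = 5.25%. If unscheduled tests caught 25% of the episodes missed by scheduled looks, the ratio would be (4.49 + 0.25 × 0.76)/(1.86 + 0.25 × 3.39) = 4.68/2.71 = 1.7. At 50% it would be 4.87/3.56 = 1.4.

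The SAP does not settle whether such tests enter the year columns. Section 7.4.3 takes in every assessment, while the unscheduled-visit rule in 11.4.3 names only the any-time-post-baseline interval.

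**The case against.** The study is descriptive, with no hypothesis tests, and worst grade over all available samples is a sound safety display because it loses nothing. The continuous by-visit summaries (SAP 7.4.2; Tables 2.56 to 2.59 and their figures) do not depend on the number of looks. They include minimum and maximum, and the schedules are printed in full in Appendix 1. All of this stands. It is why the main tables should stay and why the risk of misreading is limited. But those summaries do not show grades, so they supply neither an equal-look trend nor the by-visit Grade 3 or 4 endpoint. Only Listings 35 to 40 remain for that.

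It is also fair to say that every ratio above rests on assumed prevalence and duration. Persistent abnormalities shrink the effect almost to nothing, and 7.4.3 and 7.4.4 do not themselves state a split by parent group.

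A reader might extend the point to time to first BILAG flare, where parent-study assessments were also more frequent. The documents do not support a finding of that weight. SAP 8.2.6 already states the six-monthly limitation. SAP 8.1.4 and Table 3.4 already give the complement of the 1A/2B flare, per visit rather than cumulatively, at equal Week 24 and Week 48 visits by parent group. The worked BILAG example in 11.5.4.2 uses only those visits.

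**Conclusion.** The point holds for the laboratory grade tables. The unequal looks follow from the schedules and the year definition, and the downward tendency follows from taking a maximum. The size is not known. Under the assumptions shown, it runs from negligible for long-lasting abnormalities to about fourfold for brief ones in the most densely sampled cohort, and unscheduled tests could offset part of it.

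A reader might infer that the by-year percentages must fall several-fold, or that long-term laboratory safety cannot be judged from this plan. Neither follows: the first needs rates that the documents do not give, and the second ignores the by-visit continuous displays. The missing by-visit Grade 3 or 4 table is a gap between Section 2.2 and Appendix 12 that rests on no assumption. The change is worth making before the tables are run, but the design and main displays are not in question.

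**What to change.** Keep Tables 2.62 to 2.73 as the main display, and make four additions:

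1. Report the number of assessments per subject in each year, by laboratory panel.
2. Add a footnote that trends across years partly reflect sampling frequency.
3. State in 7.4.3 and 7.4.4 whether unscheduled tests enter the year columns, and align this with 11.4.3.
4. Add a supplementary grade summary, by visit, limited to the Week 24 and Week 48 belimumab visits. The mapping in 11.2.2 gives every cohort a haematology/chemistry look at each of these visits while it is followed. For IgG, use the one annual visit by parent study (belimumab Week 48 for BEL113750, Week 24 for BEL112341). This gives equal looks and supplies the missing by-visit Grade 3 or 4 display.

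The cost is a few SAP sentences, one footnote, one visit flag and a few extra tables from existing data. The supplement misses abnormalities between those visits, but they stay in the main tables. Its visits follow the 48-week visit year rather than the 365-day year, which a footnote should say.

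For BILAG, no extra analysis is needed. At most, add one sentence to 8.2.6 and 8.2.7 saying which assessments count.

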8. DATA ANALYSIS AND STATISTICAL CONSIDERATIONS

There is no statistical sample size calculation. All analyses will be performed using descriptive statistics and will be exploratory in nature. The data base will be locked once all subjects have completed the Week 16 follow-up visit. Immunogenicity and B cell marker data collected at the 6-month post-treatment visit will be reported separately as an addendum to the clinical study report. Details of the analysis will be given in the Reporting and Analysis Plan (RAP).

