8.1.3. Analysis of Safety Variables

AEs will be graded for severity by the investigator using Adverse Event Severity Grading Tables ([Appendix 6](#)) or the grades in Section 6.3.4, as appropriate. The frequency of AEs will be tabulated by MedDRA system organ class and preferred term and by treatment groups, according to the treatment group that the subjects were assigned to during randomisation in the BEL113750 or C1115 study. Additional analysis may be performed based on event rates adjusting for subject-years on study agent. The number of subjects with AEs and the incidence rate of AEs will be summarised in each 6-month time interval. AEs will also be summarised by MedDRA SOCs and preferred terms for those that are considered to be at least possibly related to study agent and those that are considered to be severe (Grade 3 and Grade 4). Discontinuations due to AEs will be summarised.

The frequency of laboratory abnormalities will be tabulated by treatment group. Laboratory values will be assessed for significant changes from baseline. Laboratory toxicity will be graded using Adverse Event Severity Grading Tables when possible. Shift tables will be used to determine if subjects move from normal to abnormal during the course of the study. Shifts of ≥ 2 grades and Grade 3 or Grade 4 laboratory abnormalities will be summarised.

Immunogenicity (anti-belimumab antibodies) will be summarized at baseline and during treatment and follow-up.

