2.4. Statistical Hypotheses

Since this is an open-label continuation, no formal statistical hypothesis testing will be performed. Any comparisons between the parent study randomised treatment groups will be purely descriptive.

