9.1.2. Immunoglobulin (IgG, IgA and IgM) below LLN

The number (%) of subjects with immunoglobulin (IgG, IgA and IgM) values below the lower limit of normal (LLN) will be summarised by the parent randomised treatment group, for each belimumab visit. This data will be presented separately for subjects from each parent study. See Section 11.5.5 for LLN classifications.

Additionally, the immunoglobulin data for all subjects will be shown by year interval and at "any time post-baseline". See Section 11.5.5 for LLN classifications.

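### For toxicity-graded analytes, the planned summary tables cannot tell a new Grade 2-to-3 worsening from Grade 3 already present at baseline, or Grade 3-to-4 from Grade 4 already present

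*SAP*

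**What the plan says.** - **Status of the endpoint.** SAP 2.2 puts Grade 3 or 4 laboratory abnormalities, and worsening by two or more grades, among the endpoints for the primary (safety) objective.
- **Worst grade (SAP 7.4.3, Tables 2.62–2.67).** "This reflects the worst grade for each analyte across all subjects and all assessments for each year interval and at any time post-baseline". The layout is given only as: "The display will summarize the number (%) of subjects for each of the toxicity grades". Baseline grade is not mentioned.
- **Grade shift (SAP 7.4.4, Tables 2.68–2.73).** "Toxicity grade shifts from baseline of ≥ 2 grades for each analyte will be summarized for each year interval and at any time post-baseline". The categories are "Grade 0 to 2, Grade 0 to 3, Grade 0 to 4, Grade 1 to 3, Grade 1 to 4, and Grade 2 to 4".
- **Reference-range shift (SAP 7.4.5, Tables 2.74–2.80).** These tables separate subjects who stayed low or high from those who became so, but only for tests that carry no toxicity grade.
- **Protocol 8.1.3.** "Shifts of ≥ 2 grades and Grade 3 or Grade 4 laboratory abnormalities will be summarised". The same paragraph also calls for shift tables showing movement from normal to abnormal. SAP Table 1, which lists changes from the protocol analysis, does not mention dropping these for graded tests.
- **Immunoglobulins (SAP 9.1.2).** Counts with "values below the lower limit of normal (LLN) will be summarised by the parent randomised treatment group" at each visit (Tables 5.3–5.4), and for all subjects by year interval (Table 5.5).
- **Listings (SAP 7.4.1).** All laboratory results, and separately all Grade 3 or 4 results (Listings 29–40).

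**The concern.** Every subject receives belimumab, and SAP 2.4 states that "no formal statistical hypothesis testing will be performed". Each subject's own pre-belimumab value is therefore the main reference for reading laboratory toxicity. The SAP itself allows for marked abnormality at baseline. Its Table 5 has a baseline proteinuria band of 2 mg/mg or more, while Grade 3 starts just above 2.0 mg/mg. SAP 7.2.2 plans an infection listing that includes subjects whose IgG is already Grade 3 or 4 at baseline.

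Adverse event tables are limited to treatment-emergent events (SAP 7.2.1). The worst-grade tables have no matching restriction. A Grade 3 or 4 row can therefore hold both old disease and new toxicity, and for the one-grade steps no other summary table sorts them out.

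**Working it through.** There is no planned figure to reproduce (Protocol section 8: "There is no statistical sample size calculation"). The check is an enumeration of baseline grade against worst post-baseline grade, each 0 to 4.

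**1. Is the 7.4.4 list complete for its rule?** Pairs with worst minus baseline of at least 2 are 0-2, 0-3, 0-4, 1-3, 1-4 and 2-4. That makes six, exactly the six listed, so nothing is missing under the two-grade rule.

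**2. Which routes into Grade 3/4 are tabulated against baseline?**
- From baseline Grade 0–2 there are six: 0-3, 0-4, 1-3, 1-4, 2-3, 2-4. Five are shown; 2-3 is not.
- Counting any worsening that ends in Grade 3/4 adds 3-4, giving seven. Five are shown; 2-3 and 3-4 are not.

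**3. Can the missing cells be found by subtraction?** Let n(b,w) be the number with baseline grade b and worst grade w, and assume the shift table counts each subject once, at the worst grade.
- Worst Grade 3 row: N3 = n(0,3) + n(1,3) + n(2,3) + n(3,3) + n(4,3). Subtracting the two tabulated cells leaves 2-3, 3-3 and 4-3 mixed, with any missing baselines.
- Worst Grade 4 row: N4 = n(0,4) + n(1,4) + n(2,4) + n(3,4) + n(4,4). Subtracting the three tabulated cells leaves 3-4 and 4-4 mixed, again with any missing baselines.
- New Grade 3 cases are therefore only bounded: n(0,3) + n(1,3) ≤ new ≤ N3.

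**4. How wide are the bounds?** Assume N3 = 10, with these assumed baseline splits:

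| Baseline Grade 0/1/2/3 | Shown as new (0-3 plus 1-3) | True new | Bounds from tables |
|---|---|---|---|
| 8/1/1/0 | 8 + 1 = 9 | 10 | 9 to 10 |
| 4/2/2/2 | 4 + 2 = 6 | 8 | 6 to 10 |
| 1/1/4/4 | 1 + 1 = 2 | 6 | 2 to 10 |
| 0/0/10/0 | 0 | 10 | 0 to 10 |
| 0/0/0/10 | 0 | 0 | 0 to 10 |

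The last two rows give identical worst-grade and two-grade tables, yet one is all new toxicity and the other is none.

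**5. Do other summaries fill the gap?**
- SAP 7.4.2 gives change from baseline by visit as group statistics, not by grade.
- The proteinuria shifts (SAP 8.2.10) split only at 0.5 mg/mg. A move from 1.5 to 2.5 mg/mg is Grade 2 to 3 in SAP 11.9.2, but counts there as no change.

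**6. Immunoglobulins.** SAP 11.9.1 marks IgG as graded, and IgA and IgM as ungraded.
- IgA and IgM therefore appear in Tables 2.79–2.80, which split new from persistent low values at each visit.
- IgG does not. Its lower limit is 6.94 g/L × 100 = 694 mg/dL, and Grade 1 is 550–700 mg/dL. A fall from above 700 to 600 mg/dL is newly low but only a Grade 0-to-1 shift. It is absent from 7.4.4, excluded from 7.4.5, and counted in Tables 5.3–5.5 together with subjects low at baseline.
- Table 1.32 gives the number low at baseline, but two marginal counts do not show who is new.
- Table 5.5 (year interval) has no baseline-referenced counterpart for any isotype.

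**The case against.** The strongest reply is that the SAP does what the protocol asked. The two-grade threshold is in Protocol 8.1.3 and in the SAP 2.2 endpoint, and the six categories exhaust it. That stands: the absence of 2-3 and 3-4 from Tables 2.68–2.73 is neither an error nor a departure. It does not answer the protocol's other request, for normal-to-abnormal shift tables. For graded analytes the SAP describes no general table of that kind; proteinuria at 0.5 mg/mg is an exception.

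A reader might infer that new Grade 3/4 toxicity cannot be separated from pre-existing abnormality at all. The documents do not support that. Five of six routes are tabulated against the pre-belimumab baseline, 3-to-4 is worsening within Grade 3/4 rather than a new entry, and Listings 29–40 allow each case to be resolved. A reader might also infer that every below-LLN table has the flaw. By visit, IgA and IgM are already covered.

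Clinically significant laboratory abnormalities are also recorded as adverse events (Protocol 6.3.3), and so reach the treatment-emergent tables. This helps only in part, because findings associated with the underlying disease are not reported unless more severe than expected.

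Finally, the mock shells are in a separate document (SAP 11.13) that was not available, so a baseline column in the worst-grade layout cannot be ruled out.

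**Conclusion.** The point holds in a limited form. For graded analytes, the summary tables as described cannot distinguish a 2-to-3 worsening from pre-existing Grade 3, or 3-to-4 from pre-existing Grade 4. One of the six routes from baseline Grade 0–2 into Grade 3/4 is untabulated, as are two of the seven worsening transitions that end there. The same applies to new against pre-existing low IgG, and to all isotypes by year interval.

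The practical size depends on how many subjects start at Grade 2 or above, which the documents do not give; in the assumed examples the uncertainty runs from 1 subject in 10 to all 10. No test or conduct decision is affected. What changes is whether a display serving the primary safety objective can be read without going through the listings. The conclusion rests on the SAP text, on each subject being counted once at the worst grade, and on the unseen shells not already carrying baseline grade.

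**What to change.** 1. In Tables 2.62–2.67, add a treatment-emergent Grade 3/4 row: worst post-baseline grade is 3 or 4 and higher than the baseline grade. A baseline-by-worst-grade cross-tabulation would do the same and also show persistent Grade 3 and 4. State the definition in SAP 7.4.3, including how a missing baseline is handled.
2. Leave Tables 2.68–2.73 as they are. Their titles and the SAP 2.2 endpoint specify two grades, so one-grade rows would contradict them.
3. For IgG in Tables 5.3–5.5, and for all three isotypes in Table 5.5, add the below-LLN count among subjects at or above LLN at baseline, with that group as denominator. By-visit IgA and IgM need nothing further.

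The cost is SAP wording and a few extra rows. Baseline grades are already needed for SAP 7.4.4, and no new data are required. If the mock shells already show baseline grade, item 1 reduces to one sentence in SAP 7.4.3.
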